6.18.1 Adverse Events

Adverse events (AEs) will be coded using the latest MedDRA dictionary version.

A treatment-emergent adverse event (TEAE) is defined as an AE that started on or after the start of the administration study treatment. If adverse event dates or times are incomplete and it is not clear whether the adverse event was treatment-emergent, it will be assumed to be treatment-emergent.

Where there are partial dates, if the start date and other data mean that the event could have occurred during more than one treatment, then the event will be recorded under the lowest possible active study treatment excluding placebo that the TEAE could be assigned to.

Adverse events are treatment emergent and accountable to period x treatment if they started on or after the start of the administration study treatment in period x up to the first administration of study treatment in period x+1. However, for treatment period 3, adverse events are treatment emergent and accountable to the last treatment period if they started on or after the start of the administration study treatment in the last period up to the end of the follow-up period.

If an adverse event starts in period x and continues on till after period x+1, the adverse event will be counted in period x, i.e. the period where it first occurred. If the start time of adverse event is missing, the adverse event will be taken to have started post dose.

A treatment-related TEAE is defined as a TEAE that is definitely, possibly and unlikely related to the study treatment. If the TEAE has a missing relationship it is assumed to be related to the study treatment for analysis purposes.

System organ class and preferred term will be ordered by decreasing frequency of the total number of patients with TEAEs.

A summary table will present the following:

- TEAEs (events and patients).
- Serious TEAEs (events and patients).
- Serious study treatment related TEAEs (events and patients).
- TEAEs by severity (mild/moderate/severe) (events and patients).
- TEAEs by relationship (definitely/probable/possible/unrelated) to study treatment, the pooled study treatment related category and the pooled study unrelated category (events and patients).
- TEAEs leading to withdrawal from study (patients only).
- TEAEs leading to discontinuation of study treatment (patients only).
- Study treatment related TEAEs leading to discontinuation of study treatment (patients only).
- TEAEs leading to death (patients only).

In the above summaries, if a patient experienced more than one TEAE, the patient will be counted once using the most related event for the "by relationship to study treatment" and "related to study treatment" summaries and at the worst severity for the "by severity" summary.

The following tables will be presented:

- TEAEs by system Organ Class (SOC) and Preferred Term (PT) and by treatment group.
- TEAEs by PT.
- TEAEs by SOC, PT and severity.
- TEAEs by SOC, PT and relation to study treatment.

For all of the above, SOC and PT will be presented in decreasing frequency of the total number of patients with TEAEs.

Further details of the above four tables are given below:

- 1. If a patient experienced more than one TEAE, the patient will be counted once for each SOC and once for each PT.
- 2. If a patient experienced more than one TEAE, the patient will be counted once for each PT.
- 3. If a patient experienced more than one TEAE, the patient will be counted once for each SOC and once for each PT at the worst severity.
- 4. If a patient experienced more than one TEAE, the patient will be counted once for each SOC and once for each PT using the most related event.

Adverse event data will be listed in full and this will also include a treatment emergent flag, the time of onset and cessation of event relative to first dosing of study treatment and duration of AE. All SAEs, AEs leading to withdrawal and AEs leading to study treatment discontinuation will be listed separately.

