4 RANDOMISATION

All patients consented will be assigned a screening number using the study centre's standard convention.

Patients will receive three different treatment combinations (dry powder inhaler (DPI) plus nebulised treatment) shown in Table 1 in a randomised sequence during Treatment Periods 1 to 3. All study treatments will be administered using the inhaled route. In each case, the DPI treatment will be administered first, followed immediately (within 2 minutes) by the nebulised RPL554 or placebo using a standard Jet nebuliser (PARI LC SPRINT® attached to a PARI TurboBOY® SX compressor unit). The DPI treatment will be open label and the nebulised treatment will be double blind.

TREATMENT	DPI TREATMENT	NEBULISED			
COMBINATION		TREATMENT			
1	Tiotropium 18 mcg qd	RPL554 6 mg bid			
2	Tiotropium 18 mcg qd	Placebo bid			
3	Tiotropium 18 mcg qd	RPL554 1.5 mg bid			
Abbreviation: bid=twice daily; DPI=dry powder inhaler; qd=once daily					

Table 1: Treatment Combinations in RPL554-CO-202

Patients will be equally randomised to one of six treatment sequences (using a Latin Square design with the three different potential medication combinations) before the first study treatment administration in Treatment Period 1.

Tiotropium will be provided in trade dress and will not be blinded.

RPL554 and placebo will be administered double blind. It has not been possible to completely match the placebo to RPL554, as the visual appearance is slightly different. The study personal preparing the RPL554 and placebo, placing them into the nebuliser, and supervising dosing will therefore not to blinded to treatment identity. The dosing cup on each nebuliser will be obscured with tape to visually blind the study treatment. The sponsor, Investigator (defined as Principal Investigator and all study physicians), all patients and all other research personnel (except

bioanalytical personnel performing the pharmacokinetic assays) will therefore be blinded to the treatment allocation.

The blind should be broken only if specific emergency treatment would be dictated by knowing the treatment status of the patient. If the blind needs to be broken, the Investigator should discuss it with the Sponsor's Medical monitor in advance.

Otherwise, all blinding will be maintained until all queries are resolved and the database is locked.

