6.2 Derived data

• Definition of baseline

Baseline is defined as the last non-missing value (including scheduled and unscheduled assessments) prior to the patient receiving study treatment for each of the respective study treatments.

For ECG and vital signs, time-matched baselines from Day 1 of each Treatment Period will be used for the analysis of data.

Incomplete dates

For calculation purposes, incomplete dates will be completed using worst case. Further details are detailed in the relevant sections as required.

• Non-numeric values for numeric variables

In the case where the result of a variable is recorded as ">x", " \ge x", "<x" or " \le x", then for analysis purposes a value of x will be taken. Where a range of values is quoted the midpoint of the range will be taken.

• Methods for handling withdrawals and missing data

Patients withdrawn after only one treatment period will not be included in the efficacy analyses. If a patient has baseline data missing for a parameter, within a treatment period, data for that patient and parameter will not be derived or analysed for that treatment period.

No imputation of missing data will be performed.

All available data from all dosed patients who have received study treatment will be listed and summarised. Any unscheduled or unplanned readings will be presented within the patient listings, but only the scheduled readings will be used in any summaries. If a treatment day is rescheduled due to variability in FEV_1 or other reason, the rescheduled treatment day will be listed and summarised as the valid treatment day.

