6.7.3 Diagnosis of COPD

Details of the diagnosis of COPD including date of diagnosis, date of onset of symptoms, any hospitalisations, history of a chronic cough with phlegm for at least 3 months a year for at least 2 years and number of exacerbations in the prior year (defined as needing oral steroids and/or antibiotics) taken at screening will be summarised and listed. Where possible, duration of symptoms (years) will be derived as (date of enrolment – date of symptom +1). Duration of diagnosis (years) will be derived as (date of enrolment – date of diagnosis + 1). Dates will not be imputed, instead, where days and months are missing but year known, duration can be derived from years, where months and year are known, duration can be derived using the month and year.

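### SAP 6.18.1 gives every partly dated adverse event that could belong to either active dose to 1.5 mg, which can blunt or reverse a dose-related pattern

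*SAP*

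**What the plan says.** SAP 6.18.1 assigns a TEAE to the period in which it starts, from first dosing in that period up to first dosing in the next. A special rule covers partial dates. It applies "if the start date and other data mean that the event could have occurred during more than one treatment", and then "the event will be recorded under the lowest possible active study treatment excluding placebo that the TEAE could be assigned to". No reason is given for choosing the lowest active dose.

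The general rule in SAP 6.2 is: "For calculation purposes, incomplete dates will be completed using worst case. Further details are detailed in the relevant sections as required". Worst case is not defined.

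The other missing-data rules in SAP 6.18.1 lean towards caution. Where dates or times are incomplete and "it is not clear whether the adverse event was treatment-emergent, it will be assumed to be treatment-emergent". On causality: "If the TEAE has a missing relationship it is assumed to be related to the study treatment for analysis purposes". In the patient counts, the worst severity and the most related event are used. TEAEs are tabulated by treatment group.

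**The concern.** The rule settles the choice between 1.5 mg and 6 mg in one direction only. An event that could have started under either dose is always counted at the lower one, so among ambiguous events 6 mg can lose to 1.5 mg but never gain from it. The neighbouring rules count doubtful events against the drug; here, between active doses, the doubt favours the higher dose.

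The AE tables are where a reader will compare the tolerability of the two doses. Protocol 1.1 describes the study as dose-ranging, Protocol 2.2 makes tolerability and safety a secondary objective, and Protocol 1.2 reports headache and heart-rate findings that rise with dose, although most clearly above 6 mg. Partial dates are most likely for events that start at home in the 7 to 21 day washout, and these count to the preceding period.

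**Working it through.** The plan states no figure on this point, so there is none to reproduce. The check applies the rule to every possible case.

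**Step 1: candidate treatments.**

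| Event could belong to | SAP rule | Highest active dose |
|---|---|---|
| placebo, 1.5 mg | 1.5 mg | 1.5 mg |
| placebo, 6 mg | 6 mg | 6 mg |
| 1.5 mg, 6 mg | 1.5 mg | 6 mg |
| placebo, 1.5 mg, 6 mg | 1.5 mg | 6 mg |

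**Step 2: shares among ambiguous events.** SAP 4 states: "Patients will be equally randomised to one of six treatment sequences". Across the six sequences each pair of treatments is therefore adjacent equally often. Let the true AE rates on placebo, 1.5 mg and 6 mg be p, a and b, with S = p + a + b. Assume that the chance of an ambiguous date does not depend on treatment. For ambiguity between adjacent periods, the SAP rule gives:

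- 1.5 mg share = (p + 2a + b)/(2S). The true share is a/S, so the excess is (p + b)/(2S), which is always positive.
- 6 mg share = (p + b)/(2S). The true share is b/S, so the error is (p − b)/(2S). This is zero when b = p and negative when b exceeds p.
- 6 mg minus 1.5 mg = −a/S, whatever b is. The true difference is (b − a)/S.

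Under the highest-dose rule the 6 mg share is (p + a + 2b)/(2S) and the 1.5 mg share is (p + a)/(2S), a difference of b/S. Placebo receives nothing under either rule. The rates below are assumptions, because the documents give none.

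| p:a:b | Ambiguity | True 1.5 / 6 mg | SAP rule 1.5 / 6 mg | Highest dose 1.5 / 6 mg |
|---|---|---|---|---|
| 1:1:1 | adjacent | 33% / 33% | 67% / 33% | 33% / 67% |
| 1:1:2 | adjacent | 25% / 50% | 62.5% / 37.5% | 25% / 75% |
| 1:1:3 | adjacent | 20% / 60% | 60% / 40% | 20% / 80% |
| 1:1:1 | all three periods | 33% / 33% | 100% / 0% | 0% / 100% |
| 1:1:2 | all three periods | 25% / 50% | 100% / 0% | 0% / 100% |
| 1:1:3 | all three periods | 20% / 60% | 100% / 0% | 0% / 100% |

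In every row the SAP rule shows more of these events at 1.5 mg than at 6 mg, even when the true 6 mg rate is three times higher.

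**Step 3: which ambiguities could arise.** The washout runs from the Day 3 dose, so consecutive Day 1s are 2 + 7 = 9 to 2 + 21 = 23 days apart. As an illustration, suppose that the day of onset is missing, the month is known and has 30 days, onset is equally likely on each day up to an end-of-study visit 10 days after Day 4, and no other data narrow the choice. For gaps of 9, 16 and 23 days, both active doses are candidates for about 64%, 46% and 33% of such events. Only placebo and 6 mg are candidates for about 10%, 18% and 23%.

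**Step 4: ceiling per event.** Moving one patient's only counted event from 6 mg to 1.5 mg lowers one incidence by 1/n and raises the other by 1/n. The difference changes by 2/n: 2/30 = 6.7 points, or 2/24 = 8.3 points.

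**The case against.** A reader might infer that the rule always draws events away from 6 mg. The documents do not support that. Placebo/6 mg ambiguity goes to 6 mg, and with adjacent-period ambiguity and equal true rates the 6 mg share is unchanged at 33%. Under-counting at 6 mg needs a higher true rate there than on placebo, or ambiguity across all three periods. Against placebo the rule is conservative for the drug.

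A reader might also infer that SAP 6.18.1 contradicts SAP 6.2. That too is stronger than the text allows. SAP 6.2 does not say what worst case means, does not mention dose, and leaves details to the specific sections. SAP 6.7.3 departs from it as well: "Dates will not be imputed, instead, where days and months are missing but year known". Worst case could be read as active rather than placebo, which the rule does apply.

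The trigger is narrow. Start and stop times are recorded (Protocol 8.2), data are checked and queried (Protocol 9.3), and patients are asked about AEs before the first dose of each period (Protocol 6.2.1, repeated under 6.4.3). An event reported at that point cannot belong to the treatment about to start. The AE tables are descriptive, all AEs are listed with onset relative to dosing, and scheduled vital signs, ECG and Holter data do not depend on the rule.

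These points limit the claim and its size. They do not justify choosing the lower dose when both active doses are possible. The listing also carries no mark for events placed by the rule, so its effect could not readily be seen.

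**Conclusion.** The concern holds in a limited form. Between the two active doses the attribution is one-sided and not conservative: 1.5 mg is over-counted and a dose-related AE pattern can be flattened or reversed. It is an inconsistency with an undefined principle and with the cautious rules around it.

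The practical effect is probably small. How many events will have dates that fit more than one treatment cannot be derived from the documents. The 6.7 to 8.3 points are a ceiling per event. They assume that the event truly arose on 6 mg, that 24 to 30 patients are counted on each dose, and that the patient has no other event counted in that row under either dose. Because a patient is counted once per system organ class and preferred term, a reassigned event may change nothing. This is a cheap improvement to make before database lock.

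**What to change.** In SAP 6.18.1, change the attribution from the lowest to the highest possible active treatment, and state that this is the worst case meant for AE attribution. Flag in the AE listing every event placed by this rule. If there are any, show the AE summary under both attributions.

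The second summary is needed because the highest-dose rule is a cautious convention and not an unbiased one. With equal true rates it gives 6 mg 67% of adjacent-period ambiguous events against a true 33%, and 100% when all three periods are possible. It can therefore suggest a dose relation where none exists.

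The cost is one word, one listing flag and, at most, one extra table. The 6 mg AE rate may look slightly less favourable.

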8 HANDLING OF ADVERSE EVENTS AND PREGNANCIES

8.1 Adverse Event Definitions

Adverse event is defined as any undesirable experience occurring to a patient, or worsening in a patient, during a clinical study, whether or not considered related to the study treatment. An adverse event may be any of the following:

- 1. A new illness
- 2. An exacerbation of a sign or symptom of the underlying condition under treatment or of a concomitant illness
- 3. Unrelated to participation in the clinical study or an effect of the study treatment
- 4. A combination of one or more of the above factors

No causal relationship with the study treatment is implied by the use of the term "adverse event." An exacerbation of a pre-existing condition or illness is defined as a more frequent occurrence or as an increase in the severity of the pre-existing condition or illness during the study. Planned or elective surgical or invasive procedures for pre-existing conditions that have not worsened are not adverse events. However, any complication that occurs during a planned or elective surgery is an adverse event (if the event fits the serious criteria, such as an extended hospitalisation, it will be considered to be serious). Conditions leading to unplanned surgical procedures may be adverse events.

Adverse reaction is defined as all untoward and unintended responses to study treatment related to any dose administered.

Serious adverse event (SAE) is any adverse experience that:

- Results in death
- Is life-threatening
- Requires inpatient hospitalisation or prolongation of existing hospitalisation
- Results in persistent or significant disability/incapacity, OR
- Is a congenital anomaly/birth defect
- Other medical events*

*Important medical events that may not be immediately life-threatening or result in death or hospitalisation may be considered a SAE when, based on appropriate medical judgement, they may jeopardise the patient or may require medical or surgical intervention to prevent one of the outcomes listed above.

An unexpected adverse reaction is an adverse reaction in which the nature or severity of which is not consistent with the Investigator Brochure.

Suspected unexpected serious adverse reactions (SUSAR) is any suspected adverse reaction related to the study drug that is both unexpected and serious.

8.2 **Recording and Assessing Adverse Events**

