All adverse events, whether reported spontaneously by the patient, in response to open questioning on treatment days or observed by the Investigator or his/her staff, will be recorded from informed consent until the end of study visit. The start and stop time will be recorded and adverse events will be assessed by the Investigator for the following:

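### The SAP dates adverse events by their start alone, so a worsening kept in the original record is not counted under the treatment on which it occurred

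*SAP*

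**What the plan says.** SAP 6.18.1 states that a treatment-emergent adverse event (TEAE) "is defined as an AE that started on or after the start of the administration study treatment". Events are "accountable to period x treatment if they started on or after the start of the administration study treatment in period x", and the window for period x runs up to the first dose of period x+1 (to the end of follow-up for the last period). For an event that starts in period x and carries on beyond period x+1, "the adverse event will be counted in period x, i.e. the period where it first occurred". The section has no rule for an event that becomes more severe or more frequent after a later dose.

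Protocol 8.1 is wider. It defines an adverse event as "any undesirable experience occurring to a patient, or worsening in a patient, during a clinical study". Among the kinds of adverse event it lists "An exacerbation of a sign or symptom of the underlying condition under treatment or of a concomitant illness", and it explains exacerbation as greater frequency or greater severity.

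On recording, Protocol 8.2 says that events "will be recorded from informed consent until the end of study visit", with start and stop times and an assessment of severity. Protocol 8.2.1 grades severity by how the event resolved or was tolerated. Protocol 8.2.2 lets several limited episodes be held as one intermittent event.

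**The concern.** Tolerability and safety of RPL554 on top of tiotropium is a secondary objective, and adverse events are summarised by treatment. In a crossover, a by-treatment count is only as good as the rule that assigns each event to a period. A rule that looks only at the start date does not register what a later treatment does to an event that is already open.

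Two situations matter, both with the worsening kept in the original record:

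- **Case A.** An event begins on one treatment, is still open at the next period, and worsens there. It is counted under the first treatment only.
- **Case B.** An event begins after consent but before the first dose, for example in the 7 to 21 days of screening when long acting bronchodilators have been stopped (Protocol 5.9.1), and worsens after dosing. It did not start on or after dosing, so it is not a TEAE under any treatment.

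In both cases the treatment on which the patient got worse shows nothing for that event.

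**Working it through.** The plan gives no figure on this point, so there is none to reproduce. The check compares the wording and then counts what one event changes.

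**1. Does either document force a new record at worsening?** Protocol 8.1 allows it, because an exacerbation is itself an adverse event. Protocol 8.2 does not require it for an event already open, and 8.2.2 allows recurrent episodes to stay in one record. The SAP is silent. Both ways of recording are therefore open to the site.

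**2. What the SAP rule gives when one record is kept.** Take a patient with sequence placebo then RPL554 6 mg. An event that is not severe on placebo is still open at the 6 mg period, becomes severe there, and the single record is graded severe. The patient has no other event in the same cell.

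| Patients counted | Placebo, any grade | 6 mg, any grade | Placebo, severe | 6 mg, severe |
|---|---|---|---|---|
| SAP rule, one record | 1 | 0 | 1 | 0 |
| Worsening counted where it occurs | 1 | 1 | 0 | 1 |

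The any-grade count changes in one column only. The event did begin on placebo and belongs there under either rule. In case B the 6 mg any-grade count goes from 0 to 1 and no other column changes.

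**3. Size of one event.** SAP 6.1 bases adverse event percentages on the number of patients in the analysis set. The planned range is 24 evaluable to 30 randomised, taken here as the column denominator.

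- Any grade, later treatment: 1/30 = 3.3% to 1/24 = 4.2%.
- Within the severe category only, in case A as above: one patient leaves one column and one enters the other, so that category's difference moves by 2/30 = 6.7 to 2/24 = 8.3 points.

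The any-grade figure is a maximum. The SAP counts a patient with several TEAEs once per system organ class and once per preferred term, and in the severity table "once for each SOC and once for each PT at the worst severity". If the patient already has another event in the cell, the incidence does not move.

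**4. In how many patients could the rule apply?** There are six sequences with equal allocation. RPL554 6 mg follows at least one other treatment in 4 of 6, so case A on 6 mg is possible in 4 × 24/6 = 16 of 24 patients (4 × 30/6 = 20 of 30). By symmetry the same holds for each treatment. Case B needs no earlier treatment period and could arise in any patient. These are patients in whom the rule could apply, not expected events. The documents give no rate of events that outlast a washout.

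**5. Comparison within the SAP.** For concomitant medication, SAP 6.8 assigns an item that spans two periods to the later period as well. For adverse events only the onset period counts.

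**The case against.** The strongest reply is that the protocol already deals with worsening. Protocol 8.1 makes an exacerbation an adverse event in its own right. If it is entered with its own start, the SAP's start-based rule makes it treatment-emergent and assigns it to the right period. Deterioration after long acting bronchodilators are stopped will often be worsening of COPD, which 8.1 covers directly. Protocol 9.3 refers to eCRF completion instructions that are not among the documents and may require a new entry. This stands: the problem is conditional on how sites record. A reader might infer that the SAP orders every worsening to be charged to the earlier treatment. The text does not say that; it says nothing about worsening.

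A second reply is that few events will qualify. Each period has five doses over 3 days, washout is 7 to 21 days, and Protocol 1.2 describes the common events with the suspension as generally mild. Adverse event summaries are descriptive and all events are listed. This largely stands. It is weakened by the intermittent category, which does not need continuous symptoms, and by case B, which does not need an event to outlast a washout. The listing as described gives onset, cessation and duration but does not mention the date of a change in severity, so a reader might not be able to undo a misassignment.

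A third reply is that counting a continuing event once, at onset, avoids double counting. That is reasonable for events that continue unchanged, and the rule should stay for them.

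**Conclusion.** The point holds as a minor one. SAP 6.18.1 omits the worsening part of the protocol's adverse event definition. Where a worsening stays in the original record, the event is missed for the later treatment, or is never treatment-emergent if it began before the first dose. Each such event lowers the later treatment's incidence by at most one patient, 3.3 to 4.2 percentage points.

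A reader might infer that the event moves from one treatment to the other, giving a swing of about 7 to 8 points in the pairwise difference in incidence. The documents do not support that. An event that began on placebo counts under placebo with or without the change, so overall incidence changes in one column only. A shift in two columns can occur only within a severity category, when the worsened grade is tabulated under the onset treatment.

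The conclusion assumes that worsenings are at least sometimes kept in one record, that column denominators lie between 24 and 30, and that the patient has no other event in the same cell. The number of events affected cannot be derived from the documents and is probably small.

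**What to change.** In SAP 6.18.1, define a TEAE for period x as an adverse event that starts, or worsens in severity or frequency, from the first dose of period x up to the first dose of period x+1 (to the end of follow-up for the last period). Keep the onset-period rule for events that continue unchanged.

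In the eCRF completion instructions, have a worsening entered as a new adverse event record with its own start date and severity, in line with Protocol 8.1, so that it falls in the period of worsening. The separate dated record matters because Protocol 8.2.1 grades by outcome: a grade for the earlier part of a still-open event may not be obtainable from a single record. The instructions should say that the earlier record is graded on its course up to the worsening. If they already require a new record, only the SAP wording needs to change.

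The cost is a sentence in the SAP and a line or two in the instructions. The small downside is that a worsened event appears in two periods, so event totals rise slightly.
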